6.1. Co-primary Endpoint - Week 12 IGA Response

6.1.1. Primary Analysis

- Summary: Proportion of subjects achieving IGA response at Week 12;
- Population: FAS;
- Statistical Method: CMH and normal approximation in [Section 5.2.1](#);
- Missing Data: Missing data arising due to subject dropout are considered “non-response” (see [Section 5.3.1](#)).

6.1.2. Additional/Supportive Analysis

Additional analyses of the Week 12 IGA response are:

- The proportion of subjects achieving IGA response at Week 12 will be analyzed using the CMH and normal approximation method in [Section 5.2.1](#) for the PPAS population.

- Results of proportion of subjects achieving the EASI-75 at Week 12 will be obtained from the FAS population using a tipping point analysis where all missing responses will be multiply imputed (which will consider analyses under MAR as well as MNAR as described in [Section 5.3.1](#) and [Appendix 3](#)).

6.2. Co-primary Endpoint - Week 12 EASI-75 Response

6.2.1. Primary Analysis

- Summary: Proportion of subjects achieving EASI-75 response at Week 12;
- Population: FAS;
- Statistical Method: CMH and normal approximation in [Section 5.2.1](#);
- Missing Data: Missing data arising due to subject dropout are considered “non-response” (see [Section 5.3.1](#)).

6.2.2. Additional/Supportive Analyses

Additional analyses of the Week 12 EASI-75 response are:

- The proportion of subjects achieving EASI-75 response at Week 12 will be analyzed using the CMH and normal approximation method in [Section 5.2.1](#) for the PPAS population.
- Results of proportion of subjects achieving the EASI-75 at Week 12 will be obtained from the FAS population using a tipping point analysis where all missing responses will be multiply imputed (which will consider analyses under MAR as well as MNAR as described in [Section 5.3.1](#) and [Appendix 3](#)).

6.3. Key Secondary Endpoints

6.3.1. Weeks 2, 4 and 12 NRS4 for severity Response

- Summary: Proportion of subjects with NRS4 for severity response at Weeks 2, 4 and 12;
- Population: Subjects from the (FAS, PPAS) with a baseline NRS score for severity ≥ 4 ;
- Statistical Method: CMH and normal approximation in [Section 5.2.1](#). Visit windows will be used as described in [Appendix 2](#);
- Missing Data: Two analyses will be performed:
 - Primary Analysis: Missing data arising due to subject dropout are considered “non-response”. For any other missing observations, a multiple imputation

approach based on a GLMM will be used. (see the last two paragraphs within [Section 5.3.1](#)). This analysis will be based on both the FAS and the PPAS.

- Sensitivity Analysis: All missing data will be considered as “non-response”. This analysis will be based on the FAS only.

6.3.2. Week 12 Change from Baseline in PSAAD

- Summary: Change from baseline at Week 12;
- Population: FAS, PPAS;
- Statistical Method: MMRM in [Section 5.2.3](#). As PSAAD is collected daily, data will be summarized weekly using a simple average of the values recorded within a week (see [Appendix 8](#)). In the implementation of the MMRM models, data from all weekly visits will be used;
- Missing Data: Observed Data.

6.4. Secondary Efficacy Endpoints

6.4.1. Week 8 NRS4 for severity Response

- Summary: Proportion of subjects with NRS4 for severity response at Week 8;
- Population: Subjects from the FAS with a baseline NRS score for severity ≥ 4 ;
- Statistical Method: CMH and normal approximation in [Section 5.2.1](#). Visit windows will be used as described in [Appendix 2](#);
- Missing Data: Two analyses will be performed:
 - Primary Analysis: Missing data arising due to subject dropout are considered “non-response”. For any other missing observations, a multiple imputation approach based on a GLMM will be used. (see the last two paragraphs within [Section 5.3.1](#)). This analysis will be based on both the FAS and the PPAS.
 - Sensitivity Analysis: All missing data will be considered as “non-response”. This analysis will be based on the FAS only.

6.4.2. Time to Achieve NRS4 for severity

- Summary: Time to achieve a ≥ 4 -point improvement in the pruritus NRS for severity from baseline;
- Population: Subjects from the FAS with a baseline NRS score for severity ≥ 4 ;
- Statistical Method: Analyses for Time to Event Data in [Section 5.2.5](#);

- Missing Data: See [Section 5.3.3](#).

6.4.3. Weeks 2, 4, 8 and 12 IGA Response

- Summaries:
 - Proportion of subjects with Weeks 2, 4 and 8 IGA response based on achieving clear (0) or almost clear (1) and ≥ 2 points reduction from baseline;
 - Proportion of subjects with Weeks 2, 4, 8 and 12 IGA response based on achieving clear (0);
- Population: FAS;
- Statistical Method: CMH and normal approximation in [Section 5.2.1](#);
- Missing Data: Missing data arising due to subject dropout are considered “non-response” (see [Section 5.3.1](#)).

6.4.4. Weeks 2, 4, 8 and 12 EASI-50, EASI-90, EASI-100, SCORAD50, SCORAD75 Response

- Summary: Proportion of subjects with Weeks 2, 4, 8 and 12 EASI-50, EASI-90, EASI-100, SCORAD50, SCORAD75 response;
- Population: FAS;
- Statistical Method: CMH and normal approximation in [Section 5.2.1](#);
- Missing Data: Missing data arising due to subject dropout are considered “non-response” (see [Section 5.3.1](#)).

6.4.5. Weeks 2, 4 and 8 EASI-75 Response

- Summary: Proportion of subjects with Weeks 2, 4 and 8 EASI-75 response;
- Population: FAS;
- Statistical Method: CMH and normal approximation in [Section 5.2.1](#);
- Missing Data: Missing data arising due to subject dropout are considered “non-response” (see [Section 5.3.1](#)).

6.4.6. Weeks 2, 4, 8 and 12 Change from Baseline in Total EASI Score, Total SCORAD Score, Severity of Pruritus NRS, %BSA, SCORAD (VAS) of Sleep Loss

- Summary: Change from baseline in Total EASI Score, Total SCORAD Score, Severity of Pruritus NRS, %BSA, SCORAD (VAS) of Sleep Loss at Weeks 2, 4, 8 and 12;

- Population: FAS;
- Statistical Method: MMRM in [Section 5.2.3](#);
- Missing Data: Observed Data.

6.4.7. Weeks 2, 4, 8 and 12 Response based on %BSA

- Summary: Proportion of subjects with %BSA < 5% at Weeks 2, 4, 8 and 12;
- Population: FAS;
- Statistical Method: CMH and normal approximation in [Section 5.2.1](#);
- Missing Data: Missing data arising due to subject dropout are considered “non-response” (see [Section 5.3.1](#)).

6.5. Additional PRO Endpoints

6.5.1. Weeks 2, 4, 8 and 12 Change from Baseline in PRO Endpoints

- Summary: Change from Baseline at Weeks 2, 4, 8 and 12 in PSAAD, DLQI / CDLQI, HADS (anxiety and depression), POEM, PtGA and EQ-5D-5L / EQ-5D-Y;
- Population: FAS;
- Statistical Method: MMRM in [Section 5.2.3](#). For implementing the MMRM for PSAAD score, data from all weekly visits will be used;
- Missing Data: Observed Data.

6.5.2. Weeks 2, 4, 8 and 12 PSAAD Response

- Summary: Proportion of subjects with Weeks 2, 4, 8 and 12 PSAAD response (≥ 1 -point improvement from baseline);
- Population: Subjects from the FAS with a baseline PSAAD score ≥ 1 ;
- Statistical Method: CMH and normal approximation in [Section 5.2.1](#);
- Missing Data: Missing data arising due to subject dropout are considered “non-response” (see [Section 5.3.1](#)).

6.5.3. Weeks 2, 4, 8 and 12 PtGA Response

- Summary: Proportion of subjects with Weeks 2, 4, 8 and 12 PtGA response;
- Population: Subjects from the FAS with a baseline PtGA value ≥ 2 ;
- Statistical Method: CMH and normal approximation in [Section 5.2.1](#);

- Missing Data: Missing data arising due to subject dropout are considered “non-response” (see [Section 5.3.1](#)).

6.5.4. Weeks 2, 4, 8 and 12 HADS Response in Adults

- Summaries:
 - Proportion of adult subjects achieving a score < 8 in each of the components (anxiety and depression) of the HADS score at Weeks 2, 4, 8 and 12 (among adult subjects with a score ≥ 8 at baseline);
 - Proportion of adult subjects achieving a score < 11 in each of the components (anxiety and depression) of the HADS score at Weeks 2, 4, 8 and 12 (among adult subjects with a score ≥ 11 at baseline);
- Populations:
 - Adult subjects from the FAS with a baseline corresponding component score ≥ 8 ;
 - Adult subjects from the FAS with a baseline corresponding component score ≥ 11 ;
- Statistical Method: CMH and normal approximation in [Section 5.2.1](#);
- Missing Data: Missing data arising due to subject dropout are considered “non-response” (see [Section 5.3.1](#)).

6.5.5. Weeks 2, 4, 8 and 12 DLQI Response in Adults

- Summaries:
 - Proportion of adult subjects with ≥ 4 -point improvement from baseline in the DLQI score at Weeks 2, 4, 8 and 12 (among adult subjects with a score ≥ 4 at baseline);
 - Proportion of adult subjects with a DLQI score < 2 at Weeks 2, 4, 8 and 12 (among adult subjects with a score ≥ 2 at baseline);
- Populations:
 - Adult subjects from the FAS with a baseline DLQI score ≥ 4 ;
 - Adult subjects from the FAS with a baseline DLQI score ≥ 2 ;
- Statistical Method: CMH and normal approximation in [Section 5.2.1](#);
- Missing Data: Missing data arising due to subject dropout are considered “non-response” (see [Section 5.3.1](#)).

6.5.6. Weeks 2, 4, 8 and 12 CDLQI Response in Adolescents

- Summaries:
 - Proportion of adolescent subjects with ≥ 2.5 -point improvement from baseline in the CDLQI score at Weeks 2, 4, 8 and 12 (among adolescent subjects with a score ≥ 2.5 at baseline);
 - Proportion of adolescent subjects with a CDLQI score < 2 at Weeks 2, 4, 8 and 12 (among adolescent subjects with a score ≥ 2 at baseline);
- Populations:
 - Adolescent subjects from the FAS with a baseline CDLQI score ≥ 2.5 ;
 - Adolescent subjects from the FAS with a baseline CDLQI score ≥ 2 ;
- Statistical Method: CMH and normal approximation in [Section 5.2.1](#);

Missing Data: Missing data arising due to subject dropout are considered “non-response” (see [Section 5.3.1](#)).

6.5.7. Week 12 PRO Endpoints

- Summary: Change from Baseline at Week 12 in FACIT-F, Peds-FACIT-F, and physical and mental component scores of SF-36v2 acute;
- Population: FAS;
- Statistical Method: ANCOVA in [Section 5.2.2](#);
- Missing Data: Observed Data.

6.6. PK Endpoints

Population PK data for PF-04965842 will be summarized through appropriate data tabulations, descriptive statistics, and graphical presentation. A population PK model will be developed for the purpose of estimating PK parameters. Additional details of the methodology will be captured in a separate modeling plan and the results will also be reported separately.

6.7. Subset Analyses

Summary statistics for co-primary endpoints will be presented by subgroups below.

- Age (years) group (<18 , ≥ 18 ; <40 , ≥ 40 ; <65 , ≥ 65);
- Sex (Male, Female);

- Race (White, Black or African-American, Asian, Other²);
- Region of enrollment (US/Canada/Australia, Europe);
- AD Duration (years) group (<26, ≥26);
- Baseline disease severity (moderate, severe);
- Baseline EASI group (16-25, >25);
- Baseline % BSA group (10-30, >30-50, >50);
- Previous use of systemic immunosuppressant for AD (Yes, No).

Estimates of the difference between the active dose groups and placebo, along with the 95% confidence interval (no p-value), will be presented for each defined category of each subgroup. Analyses will be performed using the normal approximation to the binomial distribution, without any adjustments for randomization strata.

The primary purpose of the subgroup analyses is to check for consistency of results across subgroups, to make sure overall results are not being driven by some subset of subjects.

Graphical display (e.g., forest plots) of the differences between treatment groups will be presented. There is no intention to have any specific inference within subgroups.

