5.2.1. Analyses of Binary Data

Binary data at each scheduled visit will be analyzed by two approaches: (1) the test of hypothesis (and the p-value) between the PF-04965842 treatment groups versus the placebo group will be conducted by the Cochran-Mantel-Haenszel (CMH) statistic adjusting for the effect of randomization strata; p-values from the CMH statistic will be used to establish the superiority of each dose of PF-04965842 to placebo in binary responses; and (2) the proportion of responders in the PF-04965842 treatment groups versus the placebo group will be summarized by the difference and its 95% confidence interval obtained by normal approximation. The difference in proportions will be calculated within each randomization stratum. The final estimate of the difference in proportions will be a weighted average of these stratum-specific estimates using CMH weights. The CMH weight w_k for stratum k ($k = 1, 2, 3, 4$) is given by,

$$w_k = \frac{\frac{n_{ik} n_{ck}}{n_{ik} + n_{ck}}}{\sum_{j=1}^4 \frac{n_{ij} n_{cj}}{n_{ij} + n_{cj}}}$$

where n refers to sample size, the subscript c refers to a comparator group (e.g., placebo) and the subscript i refers to a test group (e.g., either the low or high doses; so that two test statistics are calculated, one for each dose versus placebo). The difference is estimated as $\hat{d} = \sum_{k=1}^4 w_k (\hat{p}_{ik} - \hat{p}_{ck})$, where \hat{p} refers to the estimated relative frequency. An estimate for \hat{p} is obtained as x/n , where x is the number of responders.

Two-sided 95% confidence intervals for the difference (based on a normal approximation) are formed by:

$$\hat{d} \pm 1.96 \sqrt{\sum_{k=1}^4 w_k^2 \left(\frac{\hat{p}_{ik}(1 - \hat{p}_{ik})}{n_{ik}} + \frac{\hat{p}_{ck}(1 - \hat{p}_{ck})}{n_{ck}} \right)}$$

In the above formula for the variance of \hat{d} (under the square-root sign), when the number of responders is zero ($x = 0$), then \hat{p} will be replaced by $0.5/(n + 1)$. This change will be made only for calculating the variance of \hat{d} and not anywhere else. Estimates of the difference in proportions along with the two-sided 95% confidence interval will also be provided for the PF-04965842 200 mg QD group versus the PF-04965842 100 mg QD group. No hypotheses will be tested.

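### The subgroup intervals for the co-primary endpoints have no stated zero-responder rule, and even with the rule in SAP 5.2.1 they fall slightly short of 95% coverage for EASI-75

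*SAP*

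**What the plan says.** SAP 6.7 covers both co-primary endpoints in nine groupings. For each dose against placebo, the difference "along with the 95% confidence interval (no p-value), will be presented for each defined category of each subgroup". The method is given in one sentence: "Analyses will be performed using the normal approximation to the binomial distribution, without any adjustments for randomization strata". No section is cited and no minimum subgroup size is set. The stated aim is descriptive: "The primary purpose of the subgroup analyses is to check for consistency of results across subgroups", and "There is no intention to have any specific inference within subgroups".

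SAP 5.2.1 defines the interval for the main binary analyses as a CMH-weighted difference over four strata, with 1.96 times the square root of a weighted sum of binomial variances. The zero-responder rule follows. It opens with "In the above formula for the variance of" the weighted difference, replaces an observed rate of zero by 0.5/(n+1), and restricts itself: "This change will be made only for calculating the variance of" that estimate. There is no matching rule for an arm in which everyone responds. The main binary analyses point to this section by number; SAP 6.1.1, for example, reads "Statistical Method: CMH and normal approximation in" Section 5.2.1.

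**The concern.** The rule is tied to a stratified formula that 6.7 drops, and 6.7 does not say whether it goes too. Two programmers could produce different intervals from the same text, and the difference is largest in small subgroups, where zero placebo responders are likely. With 75 placebo subjects planned in all, levels such as under 18, 65 and over, Black or African-American and Other race may hold few of them.

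Separately, the simple normal approximation for a difference in proportions is known to cover poorly in small samples. The forest plot is the SAP's check on consistency. Intervals that cover too little exclude a common true effect somewhat too often, so subgroups can look more different than they are.

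**Working it through.** **Inputs.** From SAP 2.2: 150/150/75 subjects, so each dose against placebo is 2:1; IGA 6% on placebo and a 20-point difference (26% active); EASI-75 15% and a 30-point difference (45% active). From SAP 5.2.1: 1.96 and the 0.5/(n+1) rule. Assumed, because the documents give no subgroup sizes: 3, 5, 8, 10 and 15 placebo subjects, with twice as many on active.

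**The plan's own figures.** With the pooled two-sided 5% test and 75 versus 150:
- IGA: pooled rate (75×0.06 + 150×0.26)/225 = 0.193; null SE 0.0558; alternative SE 0.0451; (0.20 - 1.96×0.0558)/0.0451 = 2.01; power 97.8% (96.3% with continuity correction). The plan states at least 95%.
- EASI-75: pooled rate 0.35; SEs 0.0675 and 0.0579; (0.30 - 1.96×0.0675)/0.0579 = 2.90; power 99.8% (99.7% corrected). The plan states at least 99%.
- Both: 0.95×0.99 = 94.05%. The plan states at least 94%.

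The planning rates are therefore used here as the plan uses them.

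**Number of intervals.** Levels in 6.7: age 6, sex 2, race 4, region 2, AD duration 2, severity 2, EASI 2, BSA 3, prior systemic use 2, total 25. With two doses and two endpoints, 25×2×2 = 100 intervals, of which only those from small levels are affected materially.

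**Chance of no placebo responder.** (1 - placebo rate)^n for n = 3, 5, 8, 10, 15:
- IGA, 0.94^n: 83, 73, 61, 54, 40%. With all 75 placebo subjects it is about 1%.
- EASI-75, 0.85^n: 61, 44, 27, 20, 9%.

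**Two examples.** Interval: d ± 1.96×sqrt[pt(1-pt)/nt + pc(1-pc)/nc].
- 4/16 versus 0/8, d = 25 points. Without the rule the variance is 0.25×0.75/16 + 0 = 0.01172, giving 3.8 to 46.2. With the rule the placebo rate in the variance is 0.5/9 = 0.0556, which adds 0.0556×0.9444/8 = 0.00656; the total is 0.01828, giving -1.5 to 51.5. Newcombe gives -10.7 to 49.5.
- 0/6 versus 0/3. Without the rule: [0, 0]. With it: 0.0714×0.9286/6 + 0.125×0.875/3 = 0.0475, giving -42.7 to 42.7.

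**Exact coverage of the nominal 95% interval.** The probabilities of all outcome pairs from two independent binomials at the planning rates are summed over those whose interval contains the true difference.

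| Placebo/active n | 3/6 | 5/10 | 8/16 | 10/20 | 15/30 |
|---|---|---|---|---|---|
| IGA, no rule | 82.2 | 92.7 | 92.2 | 94.3 | 94.6 |
| IGA, rule | 99.0 | 96.3 | 95.0 | 97.0 | 94.6 |
| IGA, Newcombe | 96.8 | 98.0 | 96.1 | 97.4 | 95.9 |
| EASI-75, no rule | 91.9 | 91.1 | 89.7 | 92.3 | 93.2 |
| EASI-75, rule | 93.6 | 92.1 | 93.5 | 94.7 | 93.2 |
| EASI-75, Newcombe | 95.7 | 96.0 | 96.1 | 95.5 | 95.7 |
| EASI-75, Miettinen-Nurminen | 97.4 | 96.6 | 97.0 | 95.9 | 95.9 |

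Over every placebo n from 3 to 40, EASI-75 coverage is 92.1 to 94.7% with the rule, 87.6 to 94.3% without it (lowest at 6/12), and 94.5 to 96.1% with Newcombe.

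**The case against.** The strongest reply is that 5.2.1 belongs to the SAP's general methodology. Section 6.7 names the same normal approximation and removes only the stratification. With one stratum the weight is 1 and the 5.2.1 variance becomes the unstratified one. The zero rule is written in generic x and n, so it carries over unchanged. On that reading the worst figures disappear: the 82.2% IGA coverage, the [0, 0] interval and the 3.8 to 46.2 example.

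That is a sensible reading, and probably what was meant, but the text does not say it. The rule refers to a formula that 6.7 does not use, and 6.7 lacks the cross-reference that the main analyses carry.

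Other points stand and limit the finding:
- With the rule, the EASI-75 shortfall is 0.3 to 2.9 points. It shows no steady trend with size and is not confined to small subgroups (94.6% at 75/150).
- It depends on the true rates. With the rule and selected sizes of 3 to 15 placebo subjects, coverage is 93.0 to 96.7% at 10% versus 45%, and 87.2 to 93.4% at 20% versus 70%.
- Newcombe is mildly conservative for IGA, and its misses are lopsided. For EASI-75 its interval lies wholly below the true difference in 3.4 to 4.0% of samples and wholly above in 0.2 to 1.0%. With the rule, the figures are 1.9 to 3.2% below and 3.3 to 4.9% above.
- The intervals carry no p-value and feed no decision rule.

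**Conclusion.** The concern holds, as a minor point. The gap in the text does not depend on any assumption: 6.7 does not settle whether the zero-responder rule applies, and the two readings can differ on whether an interval includes zero. The coverage result rests on the planning rates, a 2:1 split within each subgroup and the assumed sizes. Under these, the rule is enough for IGA (94.6% or more) but leaves EASI-75 below 95% at every size from 3 to 40 placebo subjects, by at most about 3 points. The primary analysis, its p-values and the multiple testing procedure are not affected.

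**What to change.** In SAP 6.7, keep the point estimates and specify Newcombe (Wilson score) or Miettinen-Nurminen intervals for the unstratified subgroup differences. Neither needs a special rule for zero responders. At a minimum, add one sentence saying that the 0.5/(n+1) replacement in 5.2.1 applies to the unstratified subgroup variance, and preferably say what is done when every subject in an arm responds.

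The cost is a software option, a sentence, and a forest-plot footnote, since the subgroup rows would use a different interval method from the overall row. Expected width, truncated to ±100 points, compared with the normal approximation plus the rule:
- EASI-75 does not widen under Newcombe: 67.6 to 65.2 points at 8 placebo subjects, 49.4 to 49.1 at 15.
- IGA widens by 2 to 5 points at 5 to 15 placebo subjects: for example 56.8 to 61.6 at 8.

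Against the reading without the rule, the 4/16 versus 0/8 interval grows from about 42 to 60 points.

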6.8. Baseline and Other Summaries and Analyses

6.8.1. Baseline Summaries

Demographics, medical history, primary diagnosis, history of prior AD treatments and disease characteristics including variables defined in [Section 3.4](#) will be summarized by treatment group according to CaPS.

6.8.2. Study Conduct and Subject Disposition

Subjects' evaluation, disposition and discontinuation will be summarized according to CaPS.

6.8.3. Study Treatment Exposure

A summary of dosing compliance by treatment group will be provided.

The exposure to study drug will be summarized by the total number of days of dosing, mean / median number of days of exposure and number and percent of subjects in exposure duration categories.

² For purposes of analysis, Other will comprise the categories of American Indian or Alaska Native, Hawaiian or Other Pacific Islander, Multi-Racial and any other category reported on the CRF.

6.8.4. Concomitant Medications and Non-drug Treatments

Prior drug and non-drug treatment, concomitant drug and non-drug treatment will be summarized according to CaPS.

6.9. Safety Summaries and Analyses

Safety analyses will be based on the SAF analysis set.

All clinical AEs, SAEs, TEAEs, withdrawal due to AEs, ECGs, vital signs and safety laboratory data will be reviewed and summarized on an ongoing basis during the study to evaluate the safety of subjects.

Safety data will be presented in tabular and/or graphical format and summarized descriptively, where appropriate. All safety endpoints will be listed and summarized in accordance with CaPS. Categorical outcomes (e.g., AEs) will be summarized by subject counts and percentage. Continuous outcome (e.g., blood pressure, pulse rate, etc.) will be summarized using N, mean, median, standard deviation, etc. Change from baseline in laboratory data, ECGs and vital signs will also be summarized. Subject listings will be produced for these safety endpoints accordingly.

